International multicenter double-blind placebo-controlled randomized parallel-group clinical trial of Anaferon for children efficacy in prevention of influenza and other acute respiratory viral infections in children during the peaks of seasonal morbidity

Phase IV

Sponsor

OOO «NPF «MATERIA MEDICA HOLDING»

Protocol numberMMH-AD-008Version date:August 23, 2018ClinicalTrials.gov Id:NCT03301155

Protocol Summary

This document represents the protocol summary for the study on human subjects. The study will be carried out in accordance with ICH GCP, National Standard of the Russian Federation GOST 52379-2005 "Good Clinical Practice", Helsinki Declaration of World Medical Association, relevant requirements of the regulatory authorities as well as the study procedures.

Title of Study

International multicenter double-blind placebo-controlled randomized parallel-group clinical trial of Anaferon for children efficacy in prevention of influenza and other acute respiratory viral infections in children during the peaks of seasonal morbidity.

Phase: IV

Sponsor: OOO "NPF "Materia Medica Holding", Moscow, Russia *Protocol No.* MMH-AD-008

Objective of the study

• To obtain additional data on the efficacy and safety of 12-week course of therapy with Anaferon for children for prevention of influenza and other acute respiratory viral infections in children during the peaks of seasonal morbidity.

Endpoints

Primary endpoint

1. Time from taking the first dose of the study drug to the onset of influenza/ARVI symptoms.

Secondary endpoints

- 1. Percentage of children not falling ill with influenza or another ARVI during 4, 8, or 12week preventive course (based on medical records).
- 2. Percentage of children with the symptoms of a respiratory or ear-nose-throat bacterial infection requiring antibacterial therapy within 12-week preventive course (based on medical records).
- 3. Percentage of children hospitalized for influenza/ARVI or their complications within 12week preventive course (based on medical records).

Safety assessment

• Presence and type of adverse events, their severity, relation to investigational drug, outcomes.

Study design

Design: an international, multicenter, double-blind, placebo-controlled, randomized study in parallel groups.

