The study will enroll children of both gender from 1 month to 6 years old. Children can participate in the study regardless of the frequency of previous ARVI. A potential study participant should not be in the incubation (if known), prodromal, acute /subacute periods of any infectious disease (except for the recovery period). Schedule for enrollment of participants: during the period of a seasonal rise in influenza/ARVI incidence in the Russian Federation and the Republic of Uzbekistan. Screening and randomization of participants will be subject to availability of official information on the incidence of influenza/ARVI in the relevant study region.

The doctor makes the first visit to the participant in the medical center or at home. After parent/adoptive parent signs the information sheet (informed consent form), the doctor evaluates the possibility of the participant being included in the trial. If the child meets all the inclusion criteria and does not have all non-inclusion criteria, then he/she is included in the study, the doctor fills in the Clinical Research Form. At visit 1 (Day 1), the participant is randomized into one of two groups: the 1st group participants will take Anaferon for children according to the preventive regimen for 12 weeks; the 2nd group participants will take Placebo according to the regimen of Anaferon for 12 weeks.

In total, the study participant will be observed for 12 weeks (screening and randomization up to 1 day, preventive treatment for 12 weeks).

During the observation period at 4 (Visit 2), 8 (Visit 3), and 12 (Visit 4) weeks, three visits are planned.

Visits 2 (Week 4 ± 3 days) and 3 (Week 8 ± 3 days) are conducted in the form of a telephone survey of parents/adoptive parents about the participant's health status, presence/absence of symptoms of influenza/ARVI, possible use of antibacterial drugs and/or hospitalization during the course preventive therapy.

Visit 4 (Week 12 ± 3 days) is carried out at home or in a medical center; the doctor collects complaints, examines the participant, registers concomitant therapy, assesses the compliance of the therapy.

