If in the period from 2 to 12 weeks a participant falls ill with influenza/ARVI¹, then he prematurely completes participation in the study (as having reached the primary endpoint). A participant is considered fallen ill with influenza/ARVI if the doctor identifies the following symptoms: febrile/subfebrile body temperature, presence at least one flu-like nonspecific symptom (decreased activity/impaired behavior/weakness; headache; chills) and at least one respiratory symptom (runny nose; nasal stuffiness; hoarseness/husky voice; sore throat; cough). In this case, the doctor makes an unscheduled visit (at home or in a medical center), which is final. During the visit, the doctor carries out the procedures of Visit 4. A nasopharyngeal swab is taken to identify the most common pathogens of influenza/ARVI².

If ARVI/influenza occurs within the first seven days from the onset of preventive therapy, the disease will not be recorded as an adverse event and will not be taken into account to evaluate the efficacy of the study drug, since an early manifestation of influenza/ARVI may indicate that the participant was included in the study when he/she was in the incubation period of an infectious disease.

During the study, concomitant therapy for underlying chronic conditions, as well as routine vaccination of the participant, are allowed, with the exception of the drugs indicated in the section "Prohibited Concomitant Treatment".

Inclusion and exclusion criteria

Inclusion criteria

- 1. Children of either gender aged from 1 month to 6 years old³.
- 2. The absence of clinical symptoms of any infectious disease, but not earlier than 14 days from its onset.
- 3. Seasonal rise in ARVI incidence, confirmed by official information.
- 4. An information sheet (Informed Consent form) for the subject participation in the clinical trial signed by one parent/adopter of the patient.

Exclusion criteria

 Acute or subacute period of infectious disease of any etiology (viral, bacterial, fungal, etc.) and localization (including upper and lower respiratory tract infection, meningitis, sepsis, otitis media, urinary tract infection, intestinal infection, etc.).

¹ The symptoms associated with teething or vaccination (post-vaccination reactions and complications) are not considered as manifestations of influenza/ARVI.

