- pidotimod/imunorix
- interleukins
- synthetic immunostimulants (levamisole, alpha-glutamyl-triptophan/thymogen, etc.)
- thymus hormone-containing drugs
- herbal immunostimulants (immunal[®], etc.)
- 3. Immunosuppressants (L04).
- 4. Antineoplastic agents (L01) and hormones (L02).
- 5. Immune sera and immunoglobulins (J06).
- 6. Fenspiride (R03DX03), omalizumab (R03DX05).
- 7. Systemic corticoids (H02AB).
- 8. Homeopathic drugs.
- 9. Drugs known to cause allergic reactions in the patient.

Study design scheme

Schedule of study procedures

| Procedure/visit | Visit 1 | Visit 2 «phone» | Visit 3 «phone» | Visit 4 |
|-----------------------------------|---------|-----------------|-----------------|------------------|
| | (Day 1) | (Week 4±3 days) | (Week 8±3 days) | (Week 12±3 days) |
| Obtaining signed informed consent | + | | | |

CONFIDENTIAL

Protocol No. MMH-AD-008 23-Aug-2018

| | | | | 20 1148 2010 |
|---|---|---|---|--------------|
| form (ICF) | | | | |
| Eligibility assessment | + | | | |
| Recording concomitant medications | + | + | + | + |
| Randomization and prescription of study therapy | + | | | |
| Study drug supply | + | | | |
| Drug accountability and return, assessment of treatment compliance | | | | + |
| Evaluation of treatment safety | + | + | + | + |
| Telephone survey | | + | + | |
| Collection of nasopharyngeal swabs for PCR diagnosis* | | * Performed in case the child falls ill with influenza/ARVI during unscheduled (additional) visit with Visit 4 procedures | | |

Statistical Analysis

Samples

Statistical analysis will be carried out in the following sets:

Total set includes all participants whose parents/adoptive parents signed the Informed Consent Form.

The sample including all enrolled and randomized subjects who received at least one dose of the study drug to be used for analysis of *safety and tolerability* (*Safety population*), as all adverse events identified after the study product administration were recorded.

Full Analysis Set consists of all enrolled and randomized patients, except for those who met at least one of the following criteria:

- 1) failure to meet inclusion/non-inclusion criteria;
- 2) subject failing to take any dose of the study drug;
- 3) absence of any data on the subject after randomization.

This is the best set for the Intention-to-treat method, so it will be used in the Intention-to-treat efficacy analysis of the test therapy.

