- 3. In the case of multiple comparisons of groups among themselves, various corrections for multiplicity will be applied (Dunnett, Tukey, Scheffe, adapted Holm criterion, etc).
- 4. For more complex data structures, approaches will be used with the construction of Generalized Linear Models and / or Mixed Linear Models.
- 5. Selection of the type of distribution, refinement of the factor and covariance structures of the model is carried out using fit statistics, such as AIC (Akaike Information Criterion).

To carry out the statistical analysis and approaches specified above the following SAS procedures are suggested:

- UNIVARIATE check for normalcy of distributions compared
- CORR, MEANS calculation of descriptive statistics
- TTEST Student t-test with all modifications
- GLM analysis of general linear models for studying temporal dynamics (ANOVA, ANCOVA)
- GENMOD analysis of generalized linear models
- MIXED mixed linear model analysis
- PHREG survival analysis.

Nonparametric criteria:

Below are the main types of possible comparisons with their respective criteria:

- 1. For evaluation of time changes in parameters under comparison, the Friedman test, a nonparametric analogue of variance analysis with repeated measurements.
- 2. For frequency analysis of contingency tables $2 \times 2 \chi^2$ test (if the frequencies compared exceed 5) of exact Fisher's test (if one of the frequencies compared is < 5).
- 3. For frequency analysis of contingency tables with multiple comparisons Cochran-Mantel-Haenszel test (modification of χ^2 test for multiple comparisons).
- 4. For the frequency analysis of data on the presence / absence of an event or outcome during repeated measurements (contingency tables with dependent strata) survival analysis.

To perform the above-mentioned non-parametric statistical analysis options, it is assumed that the following SAS procedures are used:

- FREQ Friedman test, χ^2 -test and / or Fisher exact test; Cochran–Mantel–Haenszel test
- LIFETEST survival analysis
- NPAR1WAY Mann-Whitney U-test.

Safety parameters

Adverse events recorded during the study will be grouped into frequency tables by severity, seriousness and relationship with the study product.

Data presentation

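### Influenza/ARVI in the first seven days of study drug is kept out of the adverse-event record, contrary to the plan's own safety provisions, and no analysis counts it for efficacy

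*Combined protocol and SAP*

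**What the plan says.** Study design sets a seven-day window that opens at the start of preventive therapy, so after randomisation and first dose. For influenza/ARVI inside it, "the disease will not be recorded as an adverse event and will not be taken into account to evaluate the efficacy" of the study drug. The reason given is that early illness may mean the child was already incubating at entry. No severity, hospitalisation or PCR condition is attached.

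Other sections read differently:

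- **Safety assessment:** "Presence and type of adverse events, their severity, relation to investigational drug, outcomes".
- **Statistical Analysis, Samples:** the Safety population is all randomised children with at least one dose, "as all adverse events identified after the study product administration were recorded".
- **Safety parameters:** "Adverse events recorded during the study will be grouped into frequency tables by severity, seriousness and relationship with the study product".
- **Primary endpoint:** "Time from taking the first dose of the study drug to the onset of influenza/ARVI symptoms", with no later starting day.
- **Secondary endpoint 3:** "Percentage of children hospitalized for influenza/ARVI or their complications within" the 12-week course.

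The FAS exclusions do not list week-1 illness. No sensitivity or supplementary analysis is described.

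**The concern.** Followed exactly, the rule removes one class of post-dose illness from the adverse-event record. In weeks 2 to 12 the same illness is at least captured as the primary endpoint. In week 1 it is neither an endpoint nor an adverse event. The safety tables would then understate illness on study drug in children from 1 month of age.

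If the rule governs, a child hospitalised with ARVI in week 1 would appear in neither the adverse-event tables nor secondary endpoint 3, although that endpoint covers the whole course.

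On efficacy, the clock starts at the first dose, but outcome events in Days 1-7 are set aside after randomisation and no planned analysis puts them back. If early cases are mostly incubating infections, the effect over all events is smaller than the reported one, and a reader could not see by how much.

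**Working it through.** **Safety: the passages side by side.** The Safety population rests on every post-administration adverse event being recorded; Study design says one kind is not. The safety tables are to show severity, seriousness and relationship; an event that is not recorded as an adverse event has no row in them. The reason given for the rule, possible incubation, bears on relation to study drug, which the plan already assesses. The doubt therefore has a place in the plan without dropping the event.

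**Inputs.** 12-week (84-day) risk of 80% placebo and 65% Anaferon, exponential (Evaluation of sample size, section 2); 518 children per arm (Number of subjects).

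**Plan's own figures.** λ = −ln(1−P)/84 gives 0.01916 (placebo) and 0.01250 (Anaferon). Medians ln(2)/λ are 36.2 and 55.5 days, against the stated 36 and 55. The hazard ratio is 0.01250/0.01916 = 0.652. The mean risk (0.80+0.65)/2 = 0.725 matches the stated event proportion.

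**Week-1 illness.** 1−exp(−7λ) = 0.1255 and 0.0838, so 518 × (0.1255+0.0838) = 108 children. Week 1 need not follow the constant hazard, so four cases are shown, with the plan's hazards after Day 7 in each.

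**Lower base rate (assumption).** The 80%/65% rates gave 604 per-protocol children, not the current 880. If 880 still targets 437 events, mean risk is 437/880 = 0.497. Keeping the hazard ratio at 0.652, arm risks of 57.0% and 42.3% give that mean. The hazards are 0.01004 and 0.00655, and week-1 risks 0.0679 and 0.0448: 518 × 0.1127 = 58. At half hazard, 518 × (0.0345+0.0227) = 30. With equal rates, 518 × 2 × 0.0679 = 70, or 518 × 2 × 0.0345 = 36 at half the placebo rate.

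| Week-1 hazard | Ill in week 1, placebo / Anaferon | Cases, 80%/65% | Cases, risk near 50% | Hazard ratio, all events (80%/65%) |
|---|---|---|---|---|
| Plan's constant | 12.6% / 8.4% | 108 | 58 | 0.65 |
| Half in each arm | 6.5% / 4.3% | 56 | 30 | 0.65 |
| Placebo rate in both | 12.6% / 12.6% | 130 | 70 | 0.70 |
| Half placebo rate in both | 6.5% / 6.5% | 67 | 36 | 0.68 |

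**Hazard ratio.** Under the rule it is about 0.65 in every row. For the last two rows, weight the log hazard ratios by events: 130 events at 1 and 629 at 0.652 give exp[(629/759) × ln 0.652] = 0.702; 67 and 673 give exp[(673/740) × ln 0.652] = 0.678. A simulation of 300,000 per arm gave 0.701 with week-1 events counted and 0.653 with them censored (equal rates), and 0.650 against 0.649 (constant hazard).

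**Secondary endpoint 1.** Difference between arms in percentage not ill, in points, at the 80%/65% rates. If week-1 cases count as ill, the share not ill at day D is (1 − week-1 risk) × exp(−λ(D−7)); if removed, it is exp(−λ(D−7)).

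| Week-1 hazard | Week 12: counted ill / removed | Week 4: counted ill / removed |
|---|---|---|
| Plan's constant | 15.0 / 15.3 | 12.0 / 10.0 |
| Half in each arm | 15.2 / 15.3 | 11.1 / 10.0 |
| Placebo rate in both | 13.4 / 15.3 | 8.8 / 10.0 |
| Half placebo rate in both | 14.3 / 15.3 | 9.4 / 10.0 |

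From unrounded values, counting cases as ill changes the difference by 0.2 to 1.9 points at week 12 (downward here) and 0.7 to 2.0 at week 4 (either way). The week-12 sign also depends on the base rate: with 57.0%/42.3% and constant hazard, counted ill gives 57.7 − 43.0 = 14.7, and removed gives 60.4 − 46.1 = about 14.2.

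**The case against.** The seven-day rule is prespecified, applied under blind, the same in both arms, and plausibly motivated. That stands. It is why the efficacy part is minor: an absent sensitivity analysis is a gap in good practice, not an error. None of it answers the adverse-event part.

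Several stronger readings are tempting but not supported:

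- *Serious week-1 cases escape safety reporting altogether.* The document is a summary and shows no serious-event procedure at all, so one may exist elsewhere.
- *No data are kept.* The text says only that the illness is not recorded as an adverse event. The Week 4 telephone survey asks about symptoms and hospitalisation, and the case report form is not visible, so onset dates may be collected.
- *The rule inflates the primary result.* It does so only if early cases are unaffected by drug, which is the situation the rule was written for.
- *Secondary endpoint 1 could swing by up to 4.5 points at week 12.* That needs full drug effect from Day 1 and week-1 cases counted as not ill (15.3 against 10.8). Counting them as not ill does not sit well with leaving them out of account.
- *The trial loses its power.* On the 80%/65% rates, power at 880 children is 88.6% without week-1 events, above the 80% target. The event proportion behind 880 is not stated, so no shortfall can be claimed.
- *Week-1 cases leave the FAS.* Incubation is not a listed eligibility criterion; it appears only in the design narrative, qualified as applying if known.

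**Conclusion.** The adverse-event rule is wrong as written and should be fixed: it contradicts three of the plan's own safety provisions, and its rationale belongs in the causality assessment. This conclusion rests on the text and not on any rate. The number of cases does rest on assumptions: about 56 to 130 of 1036 if the 80%/65% risks hold, about 30 to 70 if 12-week risk is near 50%. The gap for week-1 hospitalisations is conditional on the seven-day rule overriding secondary endpoint 3, which the document does not settle.

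For efficacy the finding is small: no change in the hazard ratio if the drug effect is the same in week 1, at most 0.70 against 0.65 in the cases examined, and at most about 2 points on secondary endpoint 1.

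Two matters are clarification only. Study design ends participation for illness in weeks 2 to 12, while discontinuation criterion 8 has no time limit. It is also unstated whether FAS exclusion 1 reaches a child later judged to have been incubating.

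**What to change.** 1. Record influenza/ARVI with onset in Days 1-7 as an adverse event, and as serious where it qualifies. Address possible incubation in the causality assessment. Reconcile Study design with Safety assessment, Samples and Safety parameters.
2. Count week-1 hospitalisations in secondary endpoint 3, or show them in the safety tables.
3. Keep the seven-day rule for the main efficacy analysis and state one handling, for example a Day-8 landmark with week-1 cases out of both numerator and denominator of secondary endpoint 1.
4. Add one prespecified FAS sensitivity analysis counting every influenza/ARVI from the first dose, for the primary endpoint and secondary endpoint 1. Confirm that onset dates of week-1 illness are collected.
5. Clarify FAS exclusion 1, and reconcile discontinuation criterion 8 with the weeks 2 to 12 wording.

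Cost: protocol and SAP wording, some dozens to about 130 extra adverse-event entries, and one extra model and table.

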1.7 Therefore, sample size will be calculated taking into account

a. Assumption on expected effects declared in the main efficacy criterion;

1.8 calculation of sample size for two-sided test for the final analysis will be made using the formula:

$$n = \frac{\left(z_{\alpha/2} + z_{\beta}\right)^2}{(b - \delta)^2 p_1 p_2 d}$$

where **n** – total sample size of the product and placebo, **p**₁ – proportion of subjects from the total sample size in Anaferon for children group, **p**₂ – proportion of subjects from the total sample size in placebo group, **p**1=**p**2=**0.5**); **b** – effect size (calculated as **b** = **ln**(**T**₁/**T**₂)). δ – minimum clinically relevant effect δ =**ln**(1+ Δ /**T**₂); **z**_{α /2} and **z**_{β} – relevant tabular values of z-test; **d** – expected proportion of subjects reaching primary endpoint during the study.

1.9 Final sample size will be determined using the formula:

$$\mathbf{N}_{\mathrm{F}} = \mathbf{N}_{\mathrm{PP}} / (1 - \mathbf{K}_{\mathrm{B}}),$$

where N_F – final sample size; N_{PP} – result of calculation in cl. 1.8, i.e. scheduled number of children completing the study per protocol; K_B – withdrawal coefficient.

2. Assumptions on expected clinical study effects.

CONFIDENTIAL

It was initially suggested that in Anaferon for children group proportion of subjects falling ill with ARVI/influenza in 12 weeks (84 days) after the treatment onset will not exceed 65%, in placebo group will be at least 80% (conservative estimate based on the study), therefore the difference between the study arms will be less than 15%. Minimum clinically relevant difference between the groups will be 5%.

However, due to essential inability to obtain complete data on all the disease cases in all the subjects enrolled during the study (data censored, right) and necessity to determine typical time to the disease development, we will reformulate the condition on effects in the assumption of exponentially distributed disease cases:

$P_i=1-exp(-\lambda_i T),$

where P_i – proportion of ill subjects in I group, λ_i – risk of disease in I group, T – followup time.

Therefore, evaluation of risk for experimental groups is defined as

$$\lambda_i = \ln(1-P_i)/(-T),$$

median time to the event

$T_{1/2,i}=ln(2)/\lambda_i$

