At that the expected median time to the disease in placebo group is **36** days, minimum clinically relevant difference is **6** days (therefore, minimum median time for superiority is **42** days). The scheduled effect is equal to **19** days (median time to the disease in Anaferon for children group is **55** days).

Thus, the intended effect in terms of Cox model will be $\mathbf{b} = \ln(56/36) = \ln(1.53) = 0.425$, minimum clinical effect will be $\delta = \ln(42/36) = 0.154$. Based on the assumptions on the effects we will also take the presumed total proportion of subjects falling ill during the study as equal to $\mathbf{d} = 0.725$. Therefore, sufficient number of influenza/ARVI cases required to reject null hypothesis is 437, the total required number of subjects (PP) is 604 (accurate value 602.75).

As the subject recruitment covers more than one epidemic season, **blind interim analysis** will be made in each season to assess nuisance parameters of the study.

According to the above mentioned statistical terms and assumptions, sample size of each group for the final analysis will be **302** subjects for each group (PP set is **604** in total).

Given potential withdrawal of at least **15%** of the subjects at the screening and during the study for various reasons, at least **355** subjects should be enrolled in each group (**710** subjects in total, see 1.9).

Interim analysis

The analysis is made in accordance with point 2 without unblinding the treatment group.

CONFIDENTIAL

Statistical criteria

All statistical calculations will be made using the following groups of statistical criteria:

- parametric to assess continuous and interval accidental values;
- non-parametric to obtain:
 - evaluations on equality/inequality of proportions of subjects compared for various visits,
 - analysis of frequencies in features compared, and
 - evaluation of continuous and interval accidental values in case of violation of requirement on normal sample distribution.

Parametric criteria will be checked for normality of the samples compared (Kolmogorov-Smirnov test).

The following *parametric methods and approaches* are suggested:

- To evaluate differences in continuous variables obtained in one group at two different visits – Student t-test for paired samples.
- For evaluation of time changes in parameters under comparison analysis of variance (ANOVA) or covariance (ANCOVA) analysis in a modification with repeated measurements (Repeated Measures).

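### Illness in the first week is not counted for efficacy, but the planned event proportion of 0.725 covers all 84 days; if it includes first-week illness, 604 children lose about 1.7 points of power

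*Combined protocol and SAP*

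**What the plan says.** All references are to the combined protocol and SAP.

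- **Study design, first-week rule.** Illness within seven days of starting therapy "will not be taken into account to evaluate the efficacy of the study drug, since an early manifestation" might reflect infection before enrolment. The same sentence adds that "the disease will not be recorded as an adverse event".
- **Study design, endpoint window.** "If in the period from 2 to 12 weeks a participant falls ill with" influenza/ARVI, participation ends because the primary endpoint has been reached.
- **Primary endpoint.** "Time from taking the first dose of the study drug to the onset of influenza/ARVI symptoms".
- **Evaluation of sample size, point 2, rates.** For the Anaferon group, the "proportion of subjects falling ill with ARVI/influenza in 12 weeks (84 days) after the treatment onset will not exceed 65"%; the placebo figure is at least 80%.
- **Evaluation of sample size, point 2, d.** "we will also take the presumed total proportion of subjects falling ill during the study as equal to" 0.725. The "sufficient number of influenza/ARVI cases required to reject null hypothesis is 437", and the per-protocol total is 604 (710 enrolled).
- **Blinded interim analysis.** It "will be made in each season to assess nuisance parameters of the study". The Interim analysis section under Number of subjects compares the observed event frequency with the planned one and allows the sample size to be reassessed. Neither place says over which window events are counted.
- **Discontinuation criteria, item 8.** Influenza/ARVI ends participation, with no time window given.
- **Number of subjects.** 1036 randomised, about 880 completing.

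**The concern.** Events count towards efficacy over 77 days (day 8 to day 84), but the event proportion that turns 437 events into 604 children is taken over 84 days. No deduction for the first week is stated. The yield and the power attached to 604 therefore refer to a longer window than the one analysed.

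Two things are at stake. The first is the blinded review. If its planned frequency is 0.725 and the observed frequency is counted from day 8, the sides do not match: with incidence exactly as planned, a count of every case reads 0.725 and a count from day 8 reads about 0.695. The second is transparency. The exclusion is applied after randomisation and depends on the outcome. The document describes no analysis that counts every case and no first-week count by arm, and it keeps these illnesses out of the adverse events. A reader could not check what the exclusion did.

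**Working it through.** **Inputs.** Two-sided 5%, 80% power, 1:1 allocation, 65% and 80% ill over T = 84 days, exponential times, and medians of 55, 36 and 42 days (Anaferon, placebo, minimum for superiority). All are in Evaluation of sample size. The plan prints 56/36 for the effect, but its value ln(1.53) = 0.425 matches 55/36, so 55 is used.

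**Reproducing the plan.** Events = (1.960 + 0.842)² / [0.25 × (b − δ)²].
- b − δ = ln(55/42) = 0.2697 gives 431.7 events, and 431.7/0.725 = 595.5 children.
- The stated 437 events (602.75 children) imply b − δ = 0.2680.

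The plan's figures reproduce within rounding. The required events do not depend on d. At d = 0.725, 604 × 0.725 = 437.9 events.

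**Hazards.** λ = −ln(1 − P)/84:
- placebo: −ln(0.20)/84 = 0.01916 per day
- Anaferon: −ln(0.35)/84 = 0.01250 per day

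**Ill in days 1-7.** 1 − exp(−7λ) = 12.6% placebo and 8.4% Anaferon, a mean of 10.5%.

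**d on the counted window.**
- Reading A: early cases leave the per-protocol set, or stay at risk of a later countable illness. d = mean of 1 − exp(−77λ) = (0.7713 + 0.6180)/2 = 0.6946. Events: 604 × 0.6946 = 419.6.
- Reading B: early cases stay among the 604 with no later countable event. d = mean of exp(−7λ) − exp(−84λ) = 0.6204. Events: 604 × 0.6204 = 374.7.

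**Power** = Φ(√(events/4) × (b − δ) − 1.96), for 604 children:

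| b − δ | Full window (438) | Reading A (420) | Reading B (375) |
|---|---|---|---|
| 0.2697, rounded medians | 80.6% | 78.9% | 74.2% |
| 0.2680, implied by 437 | 80.1% | 78.4% | 73.7% |
| 0.2780, unrounded medians 55.46 and 42.00 | 82.9% | 81.3% | 76.8% |

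The loss is 1.6 to 1.7 points on reading A and 6.1 to 6.4 on reading B, whichever rounding is used.

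**Children needed for 437 counted events.** 437/0.6946 = about 629 (A); 437/0.6204 = about 704 (B). Both are below 880.

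**At 880 completers with the same rates.** 880 × 0.6946 = 611 events (A) and 880 × 0.6204 = 546 (B). Power is 88-92% with the first two effects and 90-93% unrounded.

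**The case against.** The strongest reply is that the loss is within planning noise. Rounding of the medians alone moves the starting power from 80.1% to 82.9%, a spread of 2.8 points, which is more than the 1.7 lost. With unrounded medians, 604 children still have 81.3% after the exclusion. The 65% and 80% are themselves bounds. All of this stands, and it is why the point is minor.

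The percentages come from a study that is not shown. If it applied the same seven-day rule, there is no loss. That stands as a condition, although the plan's wording counts from treatment onset.

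The exclusion is prespecified, has an incubation rationale and applies alike to two blinded arms. Timing the endpoint from first dose sets the time origin and does not by itself contradict a rule on which events count. That stands too. It justifies keeping the rule, but gives no reason to omit a check on it when the plan's own rates put about 8% and 13% of the arms inside it. The text is a protocol summary, so a fuller plan might hold such a check; none appears here.

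The blinded review may be said to cover the matter already. It does so only if both sides of its comparison use the counted window, which is not stated.

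A reader might infer three stronger conclusions that the documents do not support:

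- **That power is really 74%.** Reading B needs early cases to remain in a per-protocol set defined by completing therapy per protocol. Ending early by reaching the endpoint is described only for weeks 2 to 12, and discontinuation item 8, read plainly, removes first-week cases as well. In the Full Analysis Set, where such children fit more naturally, 710 × 0.6204 = 440 events, or about 81% power as an upper bound with no other losses.
- **That the trial is underpowered.** At 880 completers with the plan's rates, power is 88-93%.
- **That the hazard ratio is biased.** Under the plan's exponential model, dropping the first week leaves the ratio unchanged. The arm difference in first-week cases is modelled from the plan's rates and is not documented.

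**Conclusion.** The mismatch of windows is real and its effect is small. On the counted window d is about 0.695 instead of 0.725, 604 per-protocol children give about 420 events instead of 438, and power drops by about 1.7 points (80-81% to 78-79% rounded, 83% to 81% unrounded). The required 437 events stands, and 0.725 is the correct mean of the two stated percentages; only the window it describes is at issue.

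This rests on four assumptions: that 65% and 80% include first-week illness; that the plan's exponential model holds; that nothing else is censored within 84 days; and that 604 per-protocol children are in fact reached. On the last, first-week cases who leave would use about 10.5 points of the 15% withdrawal allowance, and the plan does not say whether the allowance was meant to cover them.

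The figure for 880 applies the stated rates to a number whose derivation is not given. Reconciling 604/710 with 880/1036 is a separate point. Severity: minor.

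**What to change.** 1. Restate d, the event yield and the power of 604 for events from day 8. Use that d, on the same window, as the planned frequency in the blinded seasonal review.
2. Add one Full Analysis Set sensitivity analysis of the primary endpoint that counts every influenza/ARVI case from the first dose. Report first-week cases by arm. Because these cases are not recorded as adverse events, state where their onset dates are kept.
3. Reconcile the Study design text (weeks 2 to 12) with discontinuation item 8 (no window), so that it is clear what happens to first-week cases and which analysis sets they enter.

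The cost is some SAP wording, one extra analysis run and, if not already captured, one onset date per first-week case. The stated power for 604 becomes slightly less favourable. No extra participants are needed.
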